Study Protocol and Statistical Analysis Plan

EFFECTIVENESS OF COMBINED AEROBIC AND STRENGTH TRAINING IN ACUTE AND CHRONIC ADAPTATIONS IN PATIENTS WITH HEART FAILURE

Date: 19/10/2017

PROTOCOL

Title

Effectiveness of combined aerobic and strength training in acute and chronic adaptations in patients with heart failure

Participants

Patients with chronic heart failure (CHF) that underwent to a hospital-based cardiac rehabilitation (CR) program in the Lisbon district Hospitals will be recruited. The study will be performed in the Cardiovascular Rehabilitation Center of the University of Lisbon (CRECUL) at the Lisbon University Stadium (EUL). The participants will be randomized into one of the following exercise groups: A) combined exercise training with more aerobic training and less strength training (CAT); B) combined exercise training with more strength training and less aerobic training (CST); Inclusion criteria: CHF patients; receiving optimal medical therapy for CHF (including an angiotensin-converting enzyme inhibitor or an angiotensin receptor blocker and a beta-blocker unless a contraindication is evident) with a stable condition for more than 1 month (no hospitalization for heart failure (HF), no change in medication, and no change in New York Heart Association (NYHA) functional class. Exclusion criteria: if they are younger than 18 years or are unable to sign informed consent; unstable angina pectoris; and orthopedic or neurological limitations to exercise. Patients will be stratified (by age and etiology) and randomized consecutively to CAT or CST in the beginning of the exercise at community. There will be 2 assessment moments (M): M0) before starting the exercise training (ExT) program (baseline) and M1) 3 month after starting the ExT.

Sample size was calculated (G-Power, Version3.1.3) assuming a difference in carotid intima-media thickness (IMT) between groups of 5% to be a clinical important difference with a SD of 0.16, $\alpha=0.05$, $1-\beta=0.95$ and an expected dropout rate of 26%. The calculations yielded a total minimum sample size of 28 participants (14 in each group).

Recruitment

Participants with established CHF after finishing in average a 3-month hospital based CR program at the Hospital will be invited and recruited to start a community based CR program at the EUL. The Clinical Director of the CR program at the Pulido de Valente Hospital and the Clinical Director of the community based CR program at the EUL, will make one of the connections to invite all the patients with the mentioned inclusion criteria to join the community based program. All patients will have access to informed consent (is attached the file of informed consent) where the entire project will be clearly explained.

Other forms to promote the recruitment in other Hospitals in the Lisbon district will be the distribution of a leaflet, with the contacts and brief information about the community based program. It will be presented and asked to each of the Clinical Director of the CR program at the Hospitals in Lisbon district the authorization to give to all the patients who completed the hospital based program the information leaflet.

All the information provided at the flyer will be online at the website of the University of Lisbon, Faculty of Human Kinetics – University of Lisbon (FMH-UL) and Faculty of Medicine – University of Lisbon.

INTRODUCTION

CHF is the major public health problem in the world [1], highly prevalent in older individuals and a major cause of disability, hospitalizations, morbidity and mortality [2]. Generally, CHF patients have reduced exercise capacity, with main symptoms of effort intolerance, early fatigue and breathlessness [3], also exhibiting increased peripheral and central chemosensitivity, and impaired sympathovagal balance with sympathetic activation (SA) predominance [4].

Understanding the oxidative metabolism and intracellular energy transfer in both skeletal and cardiac muscle, mechanisms of endothelial dysfunction, and the role of SA and inflammatory cytokines provide possible mechanistic explanations of the pathophysiologic factors involved in the development of exercise intolerance [5, 6]. It has been shown in CHF patients that increased arterial stiffness is associated with cardiovascular morbidity and mortality [7]. There are evidences that increased arterial stiffness predicts exercise intolerance in CHF patients [8].

Increased carotid IMT is associated with subclinical left ventricular (LV) myocardial dysfunction, suggesting a possible role of carotid IMT in HF risk determination [9]. CHF is associated too with endothelial dysfunction including impaired endothelium-mediated, flow-dependent dilation (FMD). Since endothelial function is thought to play an important role in coordinating tissue perfusion and modulating arterial compliance, interventions to improve endothelial dysfunction are imperative.

Systemic vasoconstriction and impaired peripheral perfusion are hallmarks in advanced CHF. While a number of factors, including increased sympathetic tone and an activated renin-angiotensin system, have been proposed to be involved in the reduced arterial vasodilatory capacity in HF, the pivotal role of the endothelium in coordinating tissue perfusion has now been recognized.

Several clinical studies have documented endothelial dysfunction of large conduit and small resistance vessels in patients with CHF. Endothelial dysfunction may affect the cardiovascular system in two ways: first, endothelial dysfunction of resistance vessels may impair peripheral perfusion, and, second, endothelial dysfunction of large conduit vessels may limit the increase in blood flow provided by the supplying large vessels and may increase impedance of the failing LV and consequently impair LV ejection fraction (LVEF). An important functional consequence of endothelial dysfunction is the inability to release nitric oxide (NO) in response to physiological stimuli such as increases in flow, reflecting impaired FMD [10]. Conversely, chronically increased blood flow enhances the release of NO in experimental models, by upregulation of NO synthase, the enzyme that uses L-arginine to generate NO.

The intermittent increases of blood flow by physical training may increase the capability of the endothelium to release NO and therefore may restore endothelial function in patients with CHF who are usually subjected to a limited degree of physical activity[5]. The dysfunctional endothelium contributes to increased vascular stiffness and impaired arterial distensibility, augmenting myocardial damage [10].

The direct relationship between exercise and vascular health is certain, but the complex set of metabolic pathways, haemodynamic effects of exercise on cardiovascular cells/tissues, and the regulation of genetic expression activated by exercise is still largely undefined [11]. The effects of aerobic and resistance exercise on clinical blood pressure might be different, because they have different mechanical characteristics. Aerobic training (AT) is characterized by the execution of cyclic exercises, carried out with large muscle groups contracting at mild to moderate intensities for a long period of time. On the other hand, strength training (ST) is characterized by the execution of exercises in which muscles from a specific body segment are contracted against a force that opposes the movement[12].

Aerobic capacity is directly related to arterial function, including endothelial function, arterial stiffness and wave reflection. In addition, coupling of arterial and cardiac function is a major determinant of aerobic capacity. Thus, poor resting arterial function likely limits aerobic capacity, but it is also possible that changes in arterial function during acute exercise may play a role. Arterial function is not only associated with aerobic capacity, but is also an independent predictor of mortality[5].

Controlled clinical trials have shown that in HF patients ExT programs improve peripheral and cardiac adaptations and also the aerobic capacity, delay the onset of anaerobic metabolism, and improve the autonomic balance [1, 13]. Apart from adaptation in maximal cardiac output, heart contractility, and stroke volume, aerobic ExT is also able to promote amelioration in the peripheral microvascular background by reducing resistance to flow, increasing the compliance of the arteries and endothelial function [13]. Abnormalities in endothelium and FMD are a key phenomenon in the blunted vasodilatory response in CHF patients. ExT enables the improvement of both basal endothelial NO formation and agonist-mediated FMD of the skeletal muscle (SM) vasculature in CHF patients. The correction of endothelial dysfunction is associated with a significant improvement in exercise capacity evidenced by a 26% increase in peak oxygen uptake ($VO_2\text{peak}$) [14].

Previous studies in HF have been show that 16.4% of 171 patients had cachexia, and the mortality at 18 months of follow-up was as high as 50% in the subset of patients with cachexia compared with 17% in those without cachexia. Cardiac cachexia is defined as an advanced stage of HF

associated with involuntary loss of at least 5% of non-oedematous body weight. And muscle wasting, also known as sarcopenia, is the loss of muscle mass (MM) and strength, whereas cachexia describes loss of weight. Distinction of the two clinical conditions might also be challenging, because cachexia and muscle wasting can co-exist in the same patient. Indeed, cachexia might lead to muscle wasting and *vice versa*, although muscle wasting can occur earlier in the course of the disease[15].

SM strength, in upper and lower limbs, are parameters that independently predict survival [16, 17, 18]. This alternative treatment should focus on increasing MM, strength and power in the limbs to improve functionality and performance [19]. SM dysfunction includes reduced cardiac contractile performance that contributes to changes in SM physiology, muscle atrophy, weakness and reduced oxidative capacity [20]. Muscle function is also enhanced in response to ST in CHF patients, including myofilament function and whole muscle [21] as well as SM oxidative capacity [21].

It's crucial that the ExT in such patients should be train the peripheral muscles effectively without producing great cardiovascular stress. An alternative treatment approach should focus on the application of specific resistance exercise program to improve body composition [22], increase the crosssectional area, muscle fibre [23], all of which counteract muscle wasting and may be cornerstone in the prevention of sarcopenia and cardiac cachexia in CHF patients [24].

ExT is a major component of rehabilitation/secondary prevention interventions, inducing significant beneficial changes in mechanisms of pathophysiology, exercise tolerance, functional capacity and QoL, while a positive impact on hospitalization and mortality reduction. There has been growing interest in the characteristics and modalities of exercise training able to induce optimal benefits. High intensity and interval mode have been shown to induce greater benefits than moderate intensity and continuous mode regimes. Considering the current body of evidence of high-intensity interval training (HIIT) in CHF, HIIT demonstrated to be more efficient, result in long term adherence, which be an important practical aspect to consider during the ExT and consequently optimized improvements in central and peripheral adaptations [25]. More studies are needed to proof their safety and benefits on this type of patients.

Additionally, there has been sound rationale for the inclusion of ST to the HIIT, which has been also shown able to yield benefits in terms of exercise capacity and QoL. It is well known that combined AT and ST is the preferred exercise intervention to reverse or attenuate the loss of MM and improve exercise and functional capacity, muscle strength in this individuals [19]. But there are underlying mechanisms from the ST in the CHF patient's peripheral capacity that remains unidentified. And isn't known what is the benefits of combine different proportions of AT and ST.

For that reason, the investigators will test two proportions in combined training, CAT and CST. There haven't been any data on the so called combined regimes, which include both aerobic exercise with HIIT and ST and the investigators will evaluate the effects of acute and chronic response.

PURPOSE

The research project will contribute to a better understanding in several aspects that are unexplained by scientific research. The purpose of this research project are:

- 1) To determine the effectiveness of a ExT programme with different proportions of CAT and CST in promoting cumulative effects in acute and chronic adaptations in CHF patients;
- 2) To identify the mechanisms of the potential improvement in effectiveness promoted by ST;

This research project is going to employ state of the art methods focusing peripheral adaptations analysis in both groups namely in echocardiography variables, cardiopulmonary exercise testing, arterial stiffness, functional physical fitness, QoL and body composition in 2 distinguished moments: M1) baseline and M2) 3 month.

Plan and Methods

This project will assess the acute and chronic effects in central and peripheral adaptations of a combined training to patients with CHF would address a number of important breaches in scientific knowledge with potential clinical benefits.

STUDY DESIGN

A longitudinal randomized control trial (RCT) research design using two distinct ExT prescriptions (CAT and CST) will be applied in CHF patients. All the same assessments will be done in two moments: M0 - baseline and M1 - 3 months after starting the ExT. The patients will be randomized into either one of the two ExT group.

Recruitment and screening will last 9 months (September 2017 to May 2018) and the patient assessment will last until August 2018. It is expected to finish the project with peer-review redaction submitted and/or accepted in December 2018 (time line attached).

The following assessments on the 4 moments will be performed at the Pulido Valente Hospital, FMH-UL and Academia de Fitness at EUL: Echocardiogram (Echo) (MyLab Alpha, ESAOTE);

cardiopulmonary exercise test (CPET) (Ergostik, Geratherm Respiratory GmbH, Bad Kissingen); arterial stiffness - Complior Analyse (ALAM Medical); Intima-media thickness - ultrasound (ESAOTE MyLanOne); body composition - dual energy radiographic absorptiometry (DXA, Hologic Explorer-W); functional physical fitness - Fullerton Functional Fitness Test; isometric strength – portable hand dynamometer JAMAR plus digital (Sammons Preston); maximal strength – 1RM and QoL questionnaire.

All assessment moments will be done in 5 days:

Day 1 – Echo will be performed at the Pulido Valente Hospital;

Day 2 and 3 – during one day and time of the ExT session at the EUL, the patient will perform the functional physical fitness tests; maximal strength; isometric strength and QoL questionnaire. In other day the investigators will perform the arterial stiffness and the IMT before the session in rest and after the ExT;

Day 4 – In FMH, the CPET and dual energy radiographic absorptiometry (DXA) exam.

Individual reports will be sent by email or delivered on paper. During the 1-year project the multidisciplinary team will have bimonthly meetings to update the study information and discuss the patient's progress.

TASK DENOMINATION

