4. INTIMA-MEDIA THICKNESS

Carotid intima media thickness (cIMT) will be defined as the distance between the leading edge of the lumen–intima interface to the leading edge of the media–adventitia interface of the far wall of the right carotid artery using an ultrasound scanner equipped (ESAOTE MyLanOne) with a linear 13 MHz probe and implemented with a previously validated radiofrequency-based tracking of arterial wall that allows a real-time determination of common carotid far-wall thickness with high spatial and temporal resolution [26]. cIMT is automatically measured, and distension curves are acquired within a segment of the carotid artery about 1 cm before the flow divider, where the operator places the region of interest. The coefficients of variation for repeated measurements in our laboratory for cIMT and diameter are reported elsewhere [26].

To evaluate the acute effects of ExT, at the pre-exercise measurement at 15 and 30-minutes rest, blood pressure (BP) was measured twice on the right upper arm using an automatic cuff in a dorsal decubitus position. If the difference in systolic BP (SBP) between the two measurements was larger than 10 mmHg, another BP measurement was performed. The final measured value was used for the analysis. Immediately after measuring BP. Post-exercise measurement was carried out with the same methods.

From this test, the investigators will study the diameter and distensibility of the artery, intima–media thickness in the carotid arteries (cIMT), PWV, brachial blood pressure, and the alpha and beta index.

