13. STATISTICAL ANALYSIS

Data will be analyzed in M0 and M1. It will be tested the data for normality and homogeneity of variance with the Shapiro Wilk and Levene's tests, respectively. Data analysis will be described according to the established purposes for this project (descriptive values: mean, standard deviation, range, % change) and comparisons of means will be used for all purposed

outcomes intra and inter groups. Baseline characteristics between groups will be evaluated with oneway ANOVA. Mixed between within subjects ANOVA will be conducted in a 2 (pre vs post ExT) design to assess efficiency of the program. When a significant interaction is observed, t tests, or Wilcoxon signed-rank tests will be used to determine where the interaction occurred.

M0 versus M1 will be compared to evaluate the changes in patients and trace the necessary timespan for such changes using General Linear Mixed Model Analysis for repeated measures with Tukey's posthoc procedure for the mean comparisons. Pearson product moment correlation coefficient or Spearman's rank correlation coefficient will be used to study the relationship between different variables by group and correlation coefficients will be compared between groups. Statistical significance will be set at an alpha level of 0.05. Other statistical procedures can be done.

Statistical analyses will be conducted using Statistical Package for the Social Sciences (SPSS) 22.0 (IBM SPSS Statistics, Chicago, IL, USA).

Data analysis will allow peer reviews publication, slide presentations and oral communications in national and international conferences, during year of 2018 and beginning of 2019 to present all the results of the project.

REFERENCES

1. R. Belardinelli, D. Georgiou, G. Cianci and A. Purcaro, *10-year exercise training in chronic heart failure: A randomized controlled trial*, J Am Coll Cardiol **60** (2012), no. 16, 1521-1528.
2. G. Loncar, S. Fülster, S. von Haehling and V. Popovic, *Metabolism and the heart: An overview of muscle, fat, and bone metabolism in heart failure*, Int J Cardiol **162** (2013), no. 2, 77-85.
3. J. Y. Tabet, P. Meurin, A. B. Driss, H. Weber, N. Renaud, A. Grosdemouge, F. Beauvais and A. Cohen-Solal, *Benefits of exercise training in chronic heart failure*, Arch Cardiovasc Dis **102** (2009), no. 10, 721-730.

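### The sample size of 28 at 95% power cannot be reproduced from the printed inputs, and the inputs needed to check it are not stated

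*Combined protocol and SAP*

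**What the plan says.** The only justification of the sample size is in the Participants section of the protocol. It names the software ("Sample size was calculated (G-Power, Version3.1.3") and the target ("assuming a difference in carotid intima-media thickness (IMT) between groups of 5% to be a clinical important difference with a SD of 0.16"), with alpha 0.05 and power 0.95. It adds "an expected dropout rate of 26"% and concludes: "The calculations yielded a total minimum sample size of 28 participants (14 in each group").

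Two other sections bear on the calculation, but neither completes it. Section 13 (Statistical Analysis) plans a repeated-measures analysis: "Mixed between within subjects ANOVA will be conducted in a 2 (pre vs post ExT) design". It gives no correlation between M0 (baseline) and M1 (3 months) and no effect size. Section 4 (Intima-Media Thickness) leaves measurement repeatability to a citation: "The coefficients of variation for repeated measurements in our laboratory for cIMT and diameter are reported elsewhere".

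**The concern.** A 5% difference set against an SD of 0.16 looks like a small standardised effect, and 14 per group is a very small trial for 95% power. cIMT is the only outcome used for sizing, so this paragraph is the whole case for 28. If the figure is wrong, a null cIMT result will be read as strong evidence against a clinically important difference when the trial may have had little chance of detecting one. If the figure is right, it rests on something the plan does not show.

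**Working it through.** **Inputs.** Participants section: difference 5%, SD 0.16, alpha 0.05, power 0.95, dropout 26%, N = 28. Not stated anywhere: the unit and reference mean of the 5%, the unit of the SD and whether it is of values or of change, the test, the sidedness, the M0–M1 correlation r, and whether 28 is before or after dropout.

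**Step 1: direct reading.** Assume that 5% means 0.05 on the scale of the SD. Then d = 0.05/0.16 = 0.3125. Power comes from the noncentral t distribution with 2n − 2 degrees of freedom and noncentrality d√(n/2).

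| | Two-sided | One-sided |
|---|---|---|
| n per group for 95% power, before dropout | 268 | 223 |
| Power, 14 per group | 12.5% | 20% |
| Power, 10 per group | 10% | 17% |

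The 10 comes from reading 28 as the number randomised: 28 × 0.74 = 20.7 evaluable. If the inflation was by 1.26 instead, 28/1.26 = 22.2, or 11 per group (10.7% two-sided). The same results hold if 0.16 is an SD of change.

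The unknown reference mean does not close the gap. Two-sided 95% power with 14 per group needs d = 1.42, a difference of 1.416 × 0.16 = 0.227. For that to be 5%, the mean would have to be 0.227/0.05, about 4.5 in the SD's own unit.

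**Step 2: gain from baseline.** Assume instead that 0.16 is the SD of raw values and that change is compared between groups, as in the planned mixed ANOVA. The SD of change is 0.16√(2(1 − r)), so the effect is 0.3125/√(2(1 − r)). Two-sided power for a difference of 0.05:

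| Assumed r | 14 per group | 10 per group |
|---|---|---|
| 0.90 | 43% | 32% |
| 0.95 | 71% | 55% |
| 0.97 | 90% | 77% |
| r needed for 95% | 0.976 | 0.983 |

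Simulation of 40,000 trials agrees: 43.1% and 90.1% for 14 per group at r = 0.90 and 0.97.

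With 14 per group the threshold is 0.970 one-sided. Two-sided, it is 0.965 if 5% is taken of an assumed mean of 1.2, and 0.984 for an assumed mean of 0.8.

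**Step 3: how 28 might have been printed.** For a repeated-measures interaction with two groups and two time points, the noncentrality is λ = 2Nf²/(1 − r). Entries that lead to 28 at 95% power are:

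- f = d/2 = 0.156 with r about 0.903, giving N = 28 directly.
- d itself entered as f = 0.3125 with r just above 0.61, giving N = 28 directly.
- f = 0.3125 with r about 0.75, giving N = 20. Dropout then makes this 10/0.74 = 13.5, rounded up to 14 per group.

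To see what these entries mean, compare λ with the change-score noncentrality for a difference in change D, which is ND²/(8·SD²(1 − r)). Equating the two gives D = 4·f·SD. So f = 0.156 is a difference in change of 4 × 0.15625 × 0.16 = 0.10, and f = 0.3125 is 4 × 0.3125 × 0.16 = 0.20. A difference of 0.05 is f = 0.078, which needs r = 0.976 for N = 28, the same threshold as in step 2.

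**The case against.** With so many inputs unstated, the most that can be shown is that 28 cannot be checked, not that it is false. If 0.16 is an SD of raw values, power with 14 per group runs from 12.5% (r = 0.5, no gain from baseline) to 95% (r = 0.976), depending on a correlation we cannot see. The repeatability of the measurement is in a source the plan cites. An interaction test with r near 0.75, followed by inflation for dropout, lands on 28 and uses every printed number, so the calculation may be under-reported rather than failed. The plan also never calls cIMT the primary outcome.

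Part of this stands. The documents do not exclude a correlation of 0.976 to 0.983, so on the raw-SD reading the 95% claim is unsupported rather than disproved. The r = 0.75 route is a plausible account of where 28 came from, and it makes 10 evaluable per group the more natural reading. It does not rescue the claim, because it needs an unprinted correlation and an effect four times a difference of 0.05. cIMT remains the only basis given for 28, whatever its formal rank.

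**Conclusion.** The concern holds. No standard calculation using only the printed inputs gives 28. If 5% means 0.05 on the SD's scale, and either baseline brings no gain or 0.16 is an SD of change, the design has about 12.5% power two-sided with 14 per group and 10% with 10, against a stated 95%. If 0.16 is of raw values, 95% requires an M0–M1 correlation of about 0.976 (14 per group) or 0.983 (10 per group). Those thresholds are for a two-sided test and a difference of 0.05; they shift with sidedness and reference mean as shown. No section supplies or supports such a correlation. This must be fixed, because the stated power is the trial's only sizing argument.

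**What to change.** 1. State the unit and reference mean of the 5%; the unit of 0.16 and whether it is of values or of change; the G-Power test and its sidedness; any M0–M1 correlation and its source; and whether 28 is before or after the 26% dropout.
2. Recompute. If a documented correlation at the level above exists, citing it settles the point.
3. If 28 is kept without such support, replace the 95% claim. Suggested text:

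> The sample size is 28 (14 per group), which [includes / does not include] the expected 26% dropout, leaving [n] evaluable per group. For a between-group difference in cIMT change of [x, unit], SD [y, of values / of change], M0–M1 correlation [r, source], [test] and [one/two]-sided alpha 0.05, power is [p]%. The detectable difference at 80% power is [d] and the expected 95% CI half-width is [h].

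Two-sided values on the SD's scale, for orientation (r = 0.9 is an assumption, to be replaced by a sourced value):

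| Evaluable per group | Baseline gain | Power for 0.05 | Detectable at 80% | Detectable at 95% | CI half-width |
|---|---|---|---|---|---|
| 14 | none | 12.5% | 0.18 | 0.23 | 0.12 |
| 14 | r = 0.9 | 43% | 0.08 | 0.10 | 0.06 |
| 10 | none | 10% | 0.21 | 0.27 | 0.15 |
| 10 | r = 0.9 | 32% | 0.095 | 0.12 | 0.07 |

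4. Report the cIMT difference with its confidence interval, and do not read non-significance as absence of a clinically important difference.

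The cost is protocol and SAP wording only, with no extra patients if 28 is kept. The drawback is that the stated power becomes much less favourable unless a very high correlation can be documented.

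### The efficacy ANOVA by default drops patients without M1 and compares unadjusted change, while the mixed model also named could keep all 28; the plan does not say which one decides.

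*Combined protocol and SAP*

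**What the plan says.** The Participants section gives a total of 28 patients, 14 per arm, and includes "an expected dropout rate of 26" per cent in the calculation. It fixes two assessments: "There will be 2 assessment moments (M): M0) before starting the exercise training (ExT) program (baseline) and M1) 3 month after starting the ExT".

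Section 13 (Statistical Analysis) gives the efficacy question to one method: "Mixed between within subjects ANOVA will be conducted in a 2 (pre vs post ExT) design to assess efficiency of the program". The following paragraph compares M0 with M1 again, to describe change and how long it takes, using "General Linear Mixed Model Analysis for repeated measures with Tukey's posthoc procedure for the mean comparisons". That sentence mentions no arm factor, no arm-by-time term and no estimation method.

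The plan does not rank the two analyses, define who is analysed, or say what happens when M1 is missing. Baseline adjustment is not mentioned. Section 13 also leaves room for further, unnamed procedures.

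**The concern.** With two arms and two visits, the arm-by-time test of a classical mixed ANOVA is a two-sample test of raw change scores. It needs both values from each patient. With no imputation planned, a patient without M1 leaves the analysis and the M0 value goes too. A likelihood-based mixed model can keep that patient.

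Two things follow. The two named analyses may rest on different patients and give different answers, with nothing to settle which counts. And the unadjusted change comparison is open to regression to the mean. If one arm loses more patients with high baseline values, its remaining patients start lower and tend to drift up relative to the other arm without any treatment effect. Unequal loss is conceivable because the arms carry different loads: section 11 has CAT on 10 high-intensity intervals and 1 strength set in months two and three, and CST on 5 intervals and 3 sets.

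**Working it through.** **Inputs from the documents.** N = 28 (14 per arm); dropout 26%; SD 0.16, no unit given; target difference 5% of IMT, no mean given; two visits.

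**Assumptions.** SD 0.16 is in mm; mean IMT is 0.7 to 1.0 mm; M0–M1 correlation ρ is 0.5 to 0.8; normal data with equal SD at both visits; no true effect.

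**1. The plan's figure and the patients with M1.** 20/(1 − 0.26) = 27.03, which rounds up to 28, so 28 is consistent with about 20 evaluable patients after dropout. (A plain two-sample comparison with difference 0.05 and SD 0.16 would need 267 per arm before dropout. That is a separate matter and nothing below depends on it.) Forward: 28 × 0.74 = 20.7, so about 21 patients with M1 and about 7 without.

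**2. Bias of the raw change comparison.** A patient x SD above the baseline mean has expected change −(1 − ρ)x. Losing the top fraction d of baselines lowers the remaining baseline mean by φ(z)/(1 − d), with z = Φ⁻¹(1 − d). The bias is (1 − ρ) times the difference between the arms' shifts.

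Adverse illustration, 36% versus 16% (average 26%):

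- d = 0.36: z = 0.358, φ = 0.374, shift = 0.374/0.64 = 0.585
- d = 0.16: z = 0.994, φ = 0.243, shift = 0.243/0.84 = 0.290
- difference = 0.295 SD

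The standard error of the change comparison is √(2(1 − ρ)) × √(1/8.96 + 1/11.76) = √(2(1 − ρ)) × 0.443 SD.

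| ρ | Bias (SD) | Bias × 0.16 | SE (SD) | Bias/SE |
|---|---|---|---|---|
| 0.5 | 0.147 | 0.024 | 0.443 | 0.33 |
| 0.7 | 0.088 | 0.014 | 0.343 | 0.26 |
| 0.8 | 0.059 | 0.009 | 0.280 | 0.21 |

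The 5% target is 0.035 to 0.05 mm on the assumed means. The bias is therefore between 0.0094/0.05 = 19% and 0.0236/0.035 = 67% of it.

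**3. Simulation at the planned size.** 14 per arm, the 5 versus 2 highest baselines lost, 20,000 trials per value of ρ:

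| ρ | Raw change: bias | Raw change: SD of estimate | Ratio |
|---|---|---|---|
| 0.5 | 0.150 | 0.430 | 0.35 |
| 0.7 | 0.096 | 0.339 | 0.28 |
| 0.8 | 0.061 | 0.275 | 0.22 |

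Type I error of the raw change test was about 6 to 7%. The likelihood estimate using all M0 values was within 0.005 SD of zero in every case. ANCOVA in patients with M1 was within 0.004 SD.

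**4. Milder cases.**

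- 31% versus 21%, still all from the top: shifts 0.511 and 0.365, difference 0.146, bias 0.146 × 0.2 to 0.146 × 0.5 = 0.03 to 0.07 SD.
- 36% versus 16%, with dropout tendency correlated only 0.3 with baseline: 0.3 × (0.059 to 0.147) = 0.02 to 0.04 SD.
- Equal dropout from the same part of the distribution: zero.

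**5. Precision.** With random dropout and 21 of 28 having M1, the variance of the arm-by-time estimate relative to patients with both values is [(1 + ρ) + (1 − ρ) × 21/28]/2. This is 0.94 at ρ = 0.5, 0.96 at 0.7 and 0.99 at 0.9, a gain of 1 to 6%.

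**The case against.** A reader might infer that the plan commits to a completers-only analysis. It does not say so; that is how the named ANOVA behaves when nothing is imputed. Dropout is not defined either. A patient who stops training may still attend M1, so 7 missing is an upper figure for the stated rate.

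A reader might also infer that 21 patients is a shortfall or that the mixed model recovers power. Neither is supported. The 28 appears to include the dropout allowance already, and step 5 shows that baseline-only patients add almost nothing.

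Nor do the documents establish that both analyses answer one question. The mixed-model sentence names no arm term, and if it were fitted as a classical repeated-measures model it would drop the same patients.

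The strongest objection is that the bias comes from the unadjusted change score, not from omitting patients: ANCOVA in patients with M1 removes it equally well. That stands, and the fix accepts ANCOVA as an equivalent. But section 13 plans no baseline adjustment, so it does not rescue the analysis as written.

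The illustration is extreme. The plan gives one dropout rate, not two, and nothing in it suggests that wall thickness drives dropout. Even then the bias is a minority of the standard error. This limits the size of the point but not the need to say which analysis decides.

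**Conclusion.** The concern holds in a limited form. The ANOVA given the efficacy question by default discards up to about 7 of 28 patients and compares unadjusted change. A second model that could keep everyone is named without an arm effect, and nothing says which result decides or who is analysed.

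The bias is conditional: it needs dropout that both differs by arm and depends on baseline. In the adverse case it is 0.06 to 0.15 SD for ρ from 0.8 to 0.5, or about 0.2 to 0.35 of the standard error. The 19 to 67% share of the target rests on the assumed mm unit and mean IMT and should not be read as an expected error. It is worth correcting because the remedy is already in the plan and costs little.

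**What to change.** - Make the already-named mixed model the single efficacy analysis, fitted by likelihood with arm, time and arm-by-time and an unstructured covariance for the two visits. Read the effect from arm-by-time.
- Include every randomised patient in the assigned arm, with all M0 values, preferably with a common baseline mean across arms. Baseline-adjusted ANCOVA in patients with M1 is an acceptable equivalent for this bias.
- Label the mixed between-within ANOVA a sensitivity analysis.
- Invite patients who stop training to the M1 assessment, and report dropout by arm.
- State the missing-data assumption and add one simple sensitivity analysis for missing M1. The model does not correct dropout that depends on the unobserved M1 value.

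The cost is a few sentences in section 13 and some effort to bring patients back for M1. No new patients are needed.
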